7.6.3 Other endpoints

All endpoints mentioned below will be presented using the FAS population.

Myocardial function

The change from baseline after 12 and 24 months in myocardial function markers as measured by Speckle Tracking (STE) and traditional echocardiography (TE) will be evaluated, comparing between treatments.

STE and TE parameters will be provided by Bioclinica according to an agreed data transfer agreement (DTA).

Summary statistics of the parameters will be presented on a per-visit basis. For all parameters (except for the categorical parameters), both the actual value as well as the change from baseline value will be presented for each treatment group and overall. For the categorical parameters, the number/percentage of observations in the different categories will be presented per visit and treatment/overall.

To visualize the effects through time graphically, the following plots will be created:

- Mean +/- SE per treatment group and overall, and individual plots will be created for GLS/LVEF values through time. Presentations are made for the actual values and the CFB values.
- Combined spaghetti plots will be created using the actual values for GLS/LVEF values through time. No spaghetti plots will be created for change from baseline. One plot will be created, using colors to discriminate both treatment groups (which combined will show the overall group).

Free plasma oxalate

Free plasma oxalate values will be analysed using the same descriptive statistics as proposed for primary endpoint, and no statistical analysis will be applied. Similar descriptive statistics per visit (absolute and change from baseline) and plots will be created.

Urinary oxalate excretion

Urinary oxalate excretion values will be analysed using the same descriptive statistics as proposed for the primary endpoint, and no statistical analysis will be applied. Similar descriptive statistics per visit (absolute and change from baseline) and plots will be created.

Urinary oxalate excretion is collected both as centrifuged and non-centrifuged. Both will be presented.

Grade of nephrocalcinosis

Descriptive statistics (frequency and percentages), including shifts from baseline (using both baselines) after 12 and 24 months of open label treatment, will be presented for the grade of nephrocalcinosis per treatment group and overall using a tabular display. Grade of nephrocalcinosis will be assessed by ultrasound images using grade values 0-3, with the following meaning:

grade 0: no echogenicity

grade 1: mild echogenicity around medullary pyramid borders

grade 2: moderate echogenicity around and inside pyramids

grade 3: severe echogenicity of entire pyramids

Grades and shifts will be summarized for left and right kidney separately. In addition, shifts will be classified (and presented) following the addendum referred to in section 11.1. Shift tables will be presented as a crosstabulation comparing baseline and 12/24 months values.

Stool

Data collected for *O.formigenes* in stool (as genotype 1 and genotype 2) will only have measurable values if above the Limit of Detection (LOD). Values below the LOD will be replaced for calculation purposes in descriptive statistics, plots and statistical analyses (see section 11.1). The proposed analyses will only be performed if there is a limited amount (<15%) of data below LOD present on-treatment. The values will be presented as '< LOD' in the listings.

Note that in case of a provided actual value lower than the LOD, it will be presented and used as is and not imputed.

Based on previous studies, it is expected that the number of subjects positive for genotype 2 at screening/baseline and throughout the study will be very low. Therefore, in case genotype 1 or 2 is not detectable in the majority of data (see above), the analysis for that genotype will not be performed and data for that genotype will then be limited to a listing. All descriptive statistics and plots will be done separately on number of *O. formigenes* genotype 1 and 2 respectively, if applicable.

Descriptive statistics will be used to present the observed and change from baseline values per treatment group and overall over time, using two baselines. Change in number of *O. formigenes* stool will be based on number of *O. formigenes* at month 24 compared to baseline in the O - O group versus the P - O group. The measurement at month 12 will be used as supportive data.

Analyses on the total number of *O. formigenes* (i.e. the sum of genotype 1 and genotype 2) may be done as post-hoc analyses, and this depends upon the number of values <LOD.

Quality of Life questionnaires

Quality of life scoring is assessed with the questionnaires SF36V2 (for adults ≥ 18 years) or CHQ/PF50 (for children ≥ 5 years). For children younger than 5 years of age, it is likely that no information from the questionnaire is available, and data will remain missing.

SF-36V2 scores are established using 8 scales (PF=Physical Functioning, RP=Role - Physical, BP=Bodily Pain, GH=General Health, VT=Vitality, SF=Social Functioning, RE=Role - Emotional, MH=Mental Health) and 2 summary measures (PCS=Physical Component Summary, and MCS=Mental Component Summary). In addition, a separate scale is available for HT=Reported Health Transition.

CHQ/PF50 are established using 13 scales (PF=Physical Functioning, RP=Role-Physical, GH=General Health perceptions, BP=Bodily Pain, FA=Family Activities, REB=Role/Social Emotional/Behavior, PT=Parental impact - Time, PE=Parental impact - Emotional, SE=Self Esteem, MH=Mental Health, BE=Behavior, FC=Family Cohesion, CH=Change in Health) and 2 summary measures (PhS=Physical Summary, and PsS=Psychosocial Summary).

Quality of life will be presented descriptively per questionnaire type, for the two treatment groups and overall, using the selection of subjects taking the specific QoL questionnaire (i.e. adults or children). Descriptive statistics of domain scales and summary scores as well as the change from baseline for both will be presented on a per-visit basis by treatment group and overall, using the calculated T-scores and the two baselines. It should be noted that results may not be comparable or combinable, if subjects in the ePHex-OLE study fall into a different age category as compared to the ePHex study and change from baseline cannot be calculated then using the ePHex baseline values.

Individual domain scales and individual summary scores will be listed additionally, raw individual question scores and intermediate calculated scores will only be kept in the associated CDISC domains. Note that for SF-36V2 the HT scale is not used in any of the domains or summary scores, and will thus will be presented separately in the descriptive table and will be listed. For CHQ/PF50, 3 subscores were not used for the calculation of the T-scores (CH, FA and FC), and will be handled similarly as the HT scale for SF36.

Missing data (missing raw score/question, missing domain scale or missing summary measures) will be handled as described in the specific quality of life questionnaire documentation, or otherwise remain missing.

Refer to the addendum mentioned in section 11.1 for the calculations.

Renal

Markers for renal function, renal tubular capacity and inflammation are the following:

- *Urine*: magnesium, phosphorus, citrate, calcium, glycolate, creatinine, urea, calcium oxalate crystals, pH, osmolality and urinary volume.
- *Blood*: magnesium, phosphorus, citrate, calcium, glycolate, BUN, ALP, bicarbonate, CRP, WBC, creatinine and cystatine C.

These markers will be presented with descriptive statistics in tabular format using the actual values and change from baseline, per visit and treatment group/overall.

These markers will be presented as endpoint for the FAS population, and will therefore not be presented in the safety laboratory summaries. They will however be combined into the same listings section.

Note that for the 24h urine concentration parameters, an additional conversion may be necessary to obtain excretion values: see the addendum as referred in section 11.1.

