4.4.1.8 Phase III Study of OC5 (OC5-DB-02)

The OC5-DB-02 (ePHex) study is a phase III double-blind, placebo-controlled, randomised multi-centre study to evaluate the long-term efficacy and safety of Oxabact OC5 in PH patients with maintained renal function but with an eGFR below the lower limit of the normal range (<90 ml/min/1.73 m²) and a total plasma oxalate concentration \geq 10 µmol/L at baseline. The overall objective with the OC5-DB-02 study is to confirm a change from baseline in plasma oxalate concentration, improved/ stabilised kidney function and myocardial function (related to decreased oxalate crystal deposits in the heart) after 52 weeks of treatment with OC5 compared to placebo. In total, 22 subjects, aged 2 years and above, will be included in the study and randomised 1:1 to receive either OC5 or placebo. The study started in January 2018, is ongoing and is being conducted at ten sites in seven countries (Germany, France, Belgium, Spain,

United Kingdom, United States and Tunisia). Twenty-five patients have been randomized and 15 patients have completed the 52-week study (as of June 2020).

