10.4 Speckle Tracking and Traditional Echocardiography

Speckle Tracking Echocardiography (STE) is currently evaluated as a method to detect and quantify effects of oxalate deposits in the heart muscle (Lagies *et al.*, 2013; Lagies *et al.*, 2019). STE is considered to be a feasible tool for discovering subtle changes of myocardial performance and identifying PH patients at risk for serious cardiac damage.

Speckle Tracking and traditional echocardiography will be performed four times during the treatment period. The examination will be performed locally using specific equipment as detailed in the site manual. Images will be interpreted centrally in a blinded manner. If the images are not meeting the quality criteria, the examination will be repeated within 4 weeks of the initial examination (except for visit 10).

Complete instructions for the collection, processing, storage and transfer of images will be provided in the imaging manual.

STE evaluations will include global longitudinal strain, including segmental changes, short-axis myocardial function, rotational displacement and apical sparing patterns. Traditional echocardiographic parameters will also be evaluated (e.g. Ejection Fraction, End Diastolic Volume, e/é, e/a, Left Ventricular End Diastolic Dimension, Fractional shortening, Tricuspid Regurgitation by Doppler as an indicator of right ventricular/pulmonary pressure.

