11.7 Vital Sign Measurements

Vital sign measurements on study include temperature and blood pressure (systolic and diastolic in a supine position), heart rate, respiratory rate (assessed after 5 minutes resting in a supine position), weight and height. Weight will be measured using a calibrated scale with the subject lightly clothed and shoes off. Height will be measured using a calibrated wall mounted stadiometer. Height should be measured at each visit for all patients where the Schwartz equation is used to determine eGFR. This would apply to children (patients under 18 years of age at the screening visit of the ePHex study) and to any patient who turn 18 either during the ePHex study or the ePHex-OLE study periods. For patients who are adults at the screening visit of the ePHex study, height for the ePHex-OLE study will be retrieved from the ePHex database using the subject ID.

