12.2 Sample Size Calculation

The sample size for this study is based on the number of subjects enrolled in the ongoing randomised, placebo-controlled double-blind ePHex study and who choose to participate in the ePHex-OLE study. The double-blind ePHex study plans to randomise approximately 22 subjects (11 subjects to Oxabact and 11 subjects to placebo). It is anticipated that approximately 18 subjects will complete the ePHex study, and approximately 16 subjects will enter into the ePHex-OLE study. Based on an anticipated 25% drop-out rate per year, it is assumed that there will be approximately 12 patients completing the 12-month-visit, and 9 patients completing the 24-month-visit. The observation period for the primary analyses of eGFR extends to 12 months in ePHex and 24 months in the ePHex-OLE study resulting in a maximum follow-up of 36 months for completers.

A supporting power analysis using a repeated measurements model in a two-sided approach with α =5%, a 1:1 allocation ratio and assuming a within patient correlation of 0,70, showed that a power greater than 90% is achieved if a difference between treatment groups of 5 ml/min/1.73 m² with a SD of 3 ml/min/1.73 m² is found. With a slightly lower difference of 4 mL/min/1.73 m² and a SD of 3 mL/min/1.73 m², or a difference of 5 mL/min/1.73 m² with a larger SD of 4 mL/min/1.73 m², the power is still above 80% (Table 11).

Table 11 Power Calculations

Standard deviation	Difference between treatment groups in eGFR (mL/min/1.73 m²)								
	3	3 4 5 6							
3	0,65635	0,88298	0,97601	0,99715					
4	0,42540	0,65635	0,83968	0,94338					
5	0,29375	0,47211	0,65635	0,80922					

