12.7 Other Endpoints

- Change from baseline in myocardial function parameters as measured by Speckle Tracking and traditional echocardiography) will be summarised descriptively over time after 12 and 24 months of open-label Oxabact treatment.

 STE results will be evaluated over time for global longitudinal strain, including segmental changes, short-axis myocardial function, rotational displacement and apical sparing patterns. Traditional echocardiographic parameters will also be evaluated over time (e.g. Ejection Fraction, End Diastolic Volume, e/é, e/a, Left Ventricular End Diastolic Dimension, Fractional shortening, Tricuspid Regurgitation by Doppler as an indicator of right ventricular/pulmonary pressure.). A positive treatment effect would be an improved myocardial function based on the above-mentioned parameters, decreased global longitudinal strain, improved rotational displacement and reduced/removed apical sparing pattern. Change from baseline in free plasma oxalate after 12 and 24 months of open-label Oxabact treatment will be described similar to the primary endpoint.
- Change from baseline in urinary oxalate excretion after 12 and 24 months of open-label Oxabact treatment will be described.
- Grade of nephrocalcinosis after 12 and 24 months of open-label Oxabact treatment will be summarised. Grade of nephrocalcinosis will be assessed by ultrasound images using grades 0-3.
- Number of *O. formigenes* during the study will be summarised over time. Summaries will present both observed and change from baseline values overall and by genotype (genotype 1, and genotype 2). In the P O group, change from second baseline will be used instead. The association between *O. formigenes* in

- stool and total plasma oxalate concentration will be evaluated using graphical displays.
- Change from baseline in Quality of Life scores as measured by SF36V2 or CHQ/PF50 questionnaires, depending on age, will be summarised over time in the two treatment groups.
- Change from baseline after 12 and 24 months of open-label Oxabact treatment in markers for renal function, renal tubular capacity and inflammation in urine and plasma will be described. Remaining time-points during the study will be presented as supportive.

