14.2.16	Summary statistics for minimum and maximum total plasma oxalate values, including change from baseline. (FAS). Two baselines.
14.2.17	Total plasma oxalate concentration (unit) percent change from baseline over time (FAS). Two baselines.

14.2.18	Frequency tabulation on subjects with 'near-normal' total plasma oxalate levels (FAS). Two baselines.
14.2.19	Mixed Repeated Measures Model result total plasma oxalate. (FAS)
14.2.20	LS estimates total plasma oxalate. (FAS)
14.2.21	Slope results total plasma oxalate. (FAS).
14.2.22	Mean (+/-SE) total plasma oxalate versus time plot, per treatment (FAS). Similar plot for change from baseline.
14.2.23	Individual total plasma oxalate versus time plot (FAS). Similar plot for change from baseline.
14.2.24	Shift plots from baseline to minimum/maximum value for total plasma oxalate. (FAS).
14.2.25	Spaghetti plots per treatment group of the actual total plasma oxalate concentration values (FAS).
14.2.26	LS mean +/- SE plot total plasma oxalate (FAS)
14.2.27	Mean (+/- SE) plots eGFR/total plasma oxalate versus time using double axes (FAS) - Two calculation methods (2009 and 2012 formulae).
14.2.28	Mean (+/- SE) plots eGFR/total plasma oxalate versus time using double axes (FAS) - Two calculation methods (2009 and 2012 formulae).
14.2.29	Descriptive statistics kidney stone events (FAS), based on AE and US, respectively
14.2.30	Incidence rate of kidney stone events (FAS), based on AE and US, respectively
14.2.31	Descriptive statistics stone frequency by subgroup (FAS)
14.2.32	Descriptive statistics US data (FAS)
14.2.33	Statistical analysis stone frequency, based on AE and US, respectively
14.2.34	Descriptive statistics STE parameters (FAS) – raw and cfb
14.2.35	Descriptive statistics traditional echocardiography parameters (FAS) – raw and cfb
14.2.36	Descriptive statistics main STE/TE parameters (LVEF/GLS) by subgroup (FAS) – raw and cfb
14.2.37	Mean (+/-SE) main STE/TE parameters (LVEF/GLS) versus time plot, per treatment (FAS)
14.2.38	Individual main STE/TE parameters (LVEF/GLS) versus time plot, per treatment (FAS)

14.2.39	Descriptive statistics free plasma oxalate (FAS) – raw and cfb
14.2.40	Descriptive statistics free plasma oxalate by subgroup (FAS) – raw and cfb
14.2.41	Mean (+/-SE) free plasma oxalate versus time plot, per treatment (FAS). Similar plot for change from baseline.
14.2.42	Individual free plasma oxalate versus time plot (FAS). Similar plot for change from baseline.

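### As the SAP is written, left-ventricular volume and dimension are summarised without size adjustment in a sample that can include growing children, so growth can appear as cardiac change

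*SAP*

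**What the plan says.** Protocol 10.4 lists the traditional echocardiographic parameters, including "Left Ventricular End Diastolic Dimension, Fractional shortening". Protocol 12.7 repeats the list for analysis: "Traditional echocardiographic parameters will also be evaluated over time (e.g. Ejection Fraction, End Diastolic Volume". The same section says that a positive treatment effect would show as better myocardial function on the listed parameters.

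SAP 7.6.3 (Myocardial function) compares treatments on change after 12 and 24 months and sets the scale: "For all parameters (except for the categorical parameters), both the actual value as well as the change from baseline value will be presented". This is done by treatment group and overall. The matching output, table 14.2.35 in SAP 12.3, is "Descriptive statistics traditional echocardiography parameters (FAS) – raw and cfb". SAP 7.1 applies both the ePHex baseline and the second baseline to echocardiography. The age subgroup in SAP 7.6.4 restricts echocardiography to LVEF and GLS.

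On the population, Protocol 4.4.1.8 says of the parent study: "In total, 22 subjects, aged 2 years and above, will be included in the study". Completers of that study form the extension. Protocol 12.2 describes the observation period as "resulting in a maximum follow-up of 36 months for completers". On size data, Protocol 11.7 says: "Height should be measured at each visit for all patients where the Schwartz equation is used to determine eGFR". It also makes weight a vital sign, and Table 5 schedules vital signs at every visit.

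**The concern.** A ventricular volume and a ventricular diameter grow with the child. Over two to three years, an unadjusted change in a growing child mixes growth with any effect of oxalate deposits or of treatment. The two cannot be separated in a table that pools children with adults.

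Three displays are exposed. The within-group and overall changes carry the growth of every child. The O-O versus P-O comparison carries it if one group holds more children. The second-baseline display also sets changes over different lengths of time side by side, because that baseline exists only for P-O subjects. At stake is the reading of two descriptive cardiac measures: growth could be taken for enlargement, or could hide a real change.

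**Working it through.** **1. Follow-up.** 12 months in ePHex plus 24 months in the extension = 36 months, which reproduces the figure in Protocol 12.2.

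**2. Search for an adjustment.** The documents express eGFR and the urinary oxalate cut-off per 1.73 m², and SAP 7.6.3 reports Quality of Life separately for adults and children. For End Diastolic Volume and Left Ventricular End Diastolic Dimension there is no index, no z-score and no age split.

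**3. Size of the growth effect.** The documents give no growth figures, so the inputs are assumptions: two illustrative children over three years, BSA = sqrt(height in cm x weight in kg / 3600), volume proportional to BSA, and dimension proportional to something between the cube root and the square root of BSA.

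| | Child A | Child B |
|---|---|---|
| Start | 115 cm, 20 kg | 140 cm, 34 kg |
| After 3 years | 133 cm, 28 kg | 160 cm, 50 kg |
| BSA (m²) | 0.80 to 1.02 | 1.15 to 1.49 |
| BSA ratio, and so volume ratio | 1.27 (+27%) | 1.30 (+30%) |
| Dimension, cube root | 1.08 (+8%) | 1.09 (+9%) |
| Dimension, square root | 1.13 (+13%) | 1.14 (+14%) |

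These are changes in a heart that is unchanged for its size.

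**4. Sensitivity to the scaling.** If instead dimension follows height and volume follows height cubed, with height growing 2% to 7% a year:
- Dimension over three years: 1.02³ = 1.06 to 1.07³ = 1.23, or +6% to +23%.
- Volume over three years: 1.02⁹ = 1.20 to 1.07⁹ = 1.84, or +20% to +84%.

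The direction is stable. The size depends on the assumptions.

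**5. Between-group effect.** SAP 2.4 reports 18 subjects included. Assume an equal split, 9 per group. With the planned 25% drop-out a year, 18 x 0.75 x 0.75 = 10.1 remain at month 24, about 5 per group. If one group has a child where the other has an adult who does not grow, the difference in mean change shifts by (child's change)/n, in percentage points of that child's starting value:
- Volume: 27/9 = 3.0 to 30/9 = 3.3 with no drop-out; 27/5 = 5.4 to 30/5 = 6.0 with planned drop-out.
- Dimension: 8/9 = 0.9 to 14/9 = 1.6 with no drop-out; 8/5 = 1.6 to 14/5 = 2.8 with planned drop-out.

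**6. Check of the remedy.** On the assumptions of step 3, volume divided by BSA shows no change, as it should. Dimension divided by BSA does not:
- Square root scaling: 1.128/1.272 = 0.887 and 1.139/1.296 = 0.879, a fall of 11-12%.
- Cube root scaling: 1.084/1.272 = 0.852 and 1.090/1.296 = 0.841, a fall of 15-16%.

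Dividing the dimension by BSA therefore over-corrects by about 11-16%, which would look like a shrinking ventricle. LVEF is a ratio of volumes, so growth cancels from it.

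**The case against.** **Unseen specifications.** The SAP never names these two parameters; they come from a list of examples in the Protocol. The values come from the imaging vendor under a data transfer agreement, and an imaging manual and programming Addendum 1 also exist. None of these is among the documents, and any could specify size-adjusted values. In table 14.2.35, raw may only mean the value as opposed to its change. This stands in part: a reader might infer that growth will certainly be reported as cardiac change, and the documents do not prove that. However, SAP 7.6.3 points to the addendum for nephrocalcinosis shifts, stool values below the detection limit, Quality of Life scoring and urine conversion, and has no such pointer for echocardiography.

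**Limited reach.** These are descriptive other endpoints without formal testing. The individual listings show age, so a careful reader can see which subjects are children. If ePHex is negative and the extension closes early, SAP 7.1 option 2 limits efficacy output to the primary and key secondary endpoints. All of this stands.

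**Randomisation.** It gives the group comparison some protection. But age is not among the stratification factors in Protocol 12.5.1, the groups are small, and the extension takes only those who completed and chose to continue. The within-group and overall columns have no such protection.

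**Two stronger readings.** A reader might infer that the plan misreports its measure of cardiac risk. The documents do not support this: Protocol 10.4 gives the role of identifying patients at risk to speckle tracking, and the SAP plots and subgroups feature GLS and LVEF. A reader might also extend the point to serum creatinine in the renal marker table. That adds little, because the primary endpoint already gives creatinine corrected for height in children.

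**Conclusion.** The point holds for the plan as written, within narrow limits. Following SAP 7.6.3 for End Diastolic Volume and Left Ventricular End Diastolic Dimension mixes growth with cardiac change wherever children contribute. The illustrative size over three years is about 27-30% for volume and 8-14% for dimension, and it rests on assumed growth and scaling. The documents do not state how many children entered the extension, so the effect on the group means is unknown. LVEF, GLS and the primary and key secondary endpoints are unaffected. This is a clarification worth making before database lock; it does not threaten the trial's main results.

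**What to change.** In SAP 7.6.3 and table 14.2.35:
- Summarise End Diastolic Volume indexed to BSA, or as a size z-score. Use height and weight from the visit nearest the echocardiogram, since Protocol Table 5 allows two weeks either side of the clinic visit at months 6, 12 and 18. For adults use the ePHex height.
- Summarise Left Ventricular End Diastolic Dimension as a size z-score in children. Do not divide it by BSA.
- Alternatively, show both parameters in separate rows for subjects under 18 and 18 or over at ePHex baseline. This does not remove growth from the children's rows, but it keeps it out of the adults' rows and makes it visible.
- If the imaging vendor already supplies size-adjusted values, state that these are the values analysed. One sentence then closes the point.

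LVEF, GLS and fractional shortening can stay as they are. The cost is one derived variable from measurements already collected, a named z-score reference if that route is taken, and a few more table rows with small counts. No new procedure or visit is needed.

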10.6 Other Parameters for Evaluation of Treatment Effect

10.6.1 Quantification of *O. formigenes*

The possibility to monitor the natural occurrence of *O. formigenes* bacteria and the presence of the *O. formigenes* drug before, during and after treatment with OC5 is an important tool for control of the pharmacodynamics of the drug. To date, two different genotypes of naturally occurring *Oxalobacter formigenes* have been identified, genotype 1 and 2 (groups I and II). Oxabact, or OC5, is of the strain HC-1 of the *O. formigenes* genotype 1. A real-time quantitative PCR assay will be used that permits determination of the numbers of both *O. formigenes* genotype 1 and genotype 2 in faecal samples.

Faecal samples will be collected at the subject's home and shipped to central laboratory MVZ Institut für Mikroökologie GmbH, Herborn, Germany.

A positive treatment effect on the result from analysis of number of *O. formigenes* should show an increased number of *O. formigenes* genotype 1 during treatment period. Earlier studies have shown that *O. formigenes* genotype 2 have increased in the OC5 treated group, but not in the placebo group indicating a transfer of oxalate from plasma to the intestine mediated by OC5 treatment. *O. formigenes* genotype 2 will also be monitored for this reason.

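### Stool analyses run only if under 15% of on-treatment values are below detection: reporting depends on the outcome, the denominator is undefined, and a second limit does not match

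*SAP*

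**What the plan says.** SAP 7.6.3, under Stool, deals with values below LOD in three steps.

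- Substitution: "Values below the LOD will be replaced for calculation purposes in descriptive statistics, plots and statistical analyses (see section 11.1". Section 11.1 refers to a separate programming addendum.
- A condition on the whole analysis: "The proposed analyses will only be performed if there is a limited amount (<15%) of data below LOD present on-treatment".
- After a short note on values reported below the LOD, a rule per genotype: "in case genotype 1 or 2 is not detectable in the majority of data (see above), the analysis for that genotype will not be performed". Such a genotype then appears only in the listings. The reason given is about genotype 2: "it is expected that the number of subjects positive for genotype 2 at screening/baseline and throughout the study will be very low". The rule itself names both genotypes.

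Analysis of the two genotypes combined is left to possible post-hoc work, again depending on how many values fall below LOD.

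The protocol is unconditional. Section 12.7 states: "Summaries will present both observed and change from baseline values overall and by genotype". It also promises a graphical evaluation of stool count against total plasma oxalate. That association is a listed endpoint in Protocol section 10 and in SAP 6.3. Protocol 10.6.1 identifies the product as genotype 1 and says that a positive effect "should show an increased number of *O. formigenes* genotype 1 during treatment period".

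SAP section 8 declares several departures from the protocol, among them the PH-type subgroup, the pattern-mixture analysis and the per-patient slope regression. The LOD condition is not among them. In SAP 12.3, Table 14.2.47 is listed without the condition. Listing 16.2.6.5 keeps the individual stool values.

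**The concern.** For genotype 1 during treatment, a value below LOD is not just an assay difficulty. It means that the organism given was not found, which is the unfavourable result on the protocol's own definition. A rule that stops the analysis once such values reach 15% makes reporting depend on the result: the poorer the colonisation, the surer it is that the summary, the change from baseline and the plots are not produced.

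This endpoint is how the protocol checks that the product reaches and persists in the gut. If plasma oxalate and eGFR did not move, readers would want to know whether treated subjects carried the organism. That is when the summary is most likely to be missing.

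Two drafting faults add to this. The limits of 15% and a majority differ, although the second refers back to the first. And nothing says what the 15% is a percentage of.

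**Working it through.** **Inputs.** 18 subjects included (SAP 2.4); 25% drop-out per year (SAP 2.4); four on-treatment stool samples, at months 6, 12, 18 and 24 (Protocol 6.3.2). The documents give no expected non-detection rate, so a range is assumed below.

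**The plan's own figures.** 16 × 0.75 = 12 completers at month 12 and 16 × 0.75² = 9 at month 24, as SAP 2.4 states.

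**Number of samples.** Without drop-out, 18 × 4 = 72. With drop-out at a constant yearly rate (the interpolation to months 6 and 18 is my assumption), each subject contributes on average 0.75^0.5 + 0.75 + 0.75^1.5 + 0.75² = 0.866 + 0.750 + 0.650 + 0.563 = 2.828 samples, so 18 × 2.828 = 50.9, about 51.

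**Where each limit bites**, taking the denominator as all on-treatment samples of one genotype, both groups and all visits together:

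| Basis | Values | Fewest below LOD that reach 15% | Fewest that make a majority |
|---|---|---|---|
| 18 subjects, no drop-out | 72 | 11 (15.3%) | 37 |
| 16 subjects, no drop-out | 64 | 10 (15.6%) | 33 |
| 18 subjects, 25% yearly drop-out | about 51 | 8 (15.7%) | 26 |

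With 72 values, the limits therefore differ for any count from 11 to 36 (15.3% to 50.0%).

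**In subjects.** Take a subject as persistently negative if every sample is below LOD.

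- Two of 18: 8/72 = 11.1%, so the analysis runs. If the two drop out at the same rate as the rest, 2 × 2.828 = 5.66 and 5.66/50.9 = 11.1%, the same.
- Three of 18: 12/72 = 16.7%, so it does not run.
- A majority needs ten: 40/72 = 55.6%. Nine give exactly 50.0%.

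**Chance of losing the analysis.** If each of 18 subjects is persistently negative with probability q, independently, and none drops out, the 15% limit is reached with probability P(X ≥ 3) and the majority limit with P(X ≥ 10), where X is binomial(18, q):

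| Assumed q | 15% limit | Majority limit |
|---|---|---|
| 10% | 27% | about 0% |
| 20% | 73% | 0.1% |
| 30% | 94% | 2% |
| 50% | 99.9% | 41% |

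Which limit is meant therefore largely decides whether the endpoint is summarised.

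**Denominator.** The SAP does not say whether the 15% is per genotype, group or visit, or pooled. Three readings matter:

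- If the genotypes were pooled, genotype 2, which the SAP expects to be rare, could alone exceed 15%.
- SAP 7.1 pools ePHex and ePHex-OLE efficacy data. If placebo-phase samples of the P-O group counted, the limit could be passed whatever happened on Oxabact.
- The majority sentence refers to data in general. That could take in the post-treatment sample, which Protocol 6.3.3 leads one to expect will usually be undetectable.

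**The case against.** The best defence is that a limit is reasonable. Means and changes computed with substituted values become artefacts of the substitution when many values are below LOD. The rule is prespecified, the endpoint is supportive, the study is descriptive without formal testing, and each value stays in Listing 16.2.6.5, marked as below LOD, with the treatment group. With 18 subjects a reader could count detections by hand. This stands as an argument for limiting substitution-based statistics. It does not justify withholding a detection frequency or a median, neither of which needs a substituted value while most values are detectable; the frequency never does.

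Several stronger readings are tempting, and the documents do not support them.

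- A reader might infer that the SAP gives opposite instructions between 15% and 50%. It does not: the first sentence is a necessary condition, and the majority sentence never says that the analysis runs in that range. Its back-reference may even mean the same rule, loosely worded. The limits are inconsistent, but there is no direct contradiction. Reading them as one rule leaves the dependence on outcome untouched.
- A reader might infer that two never-colonised subjects are enough. On a consistent denominator they are 11.1%. Two could reach the limit only if both gave all four samples while others dropped out, and even then only just: 8/(8 + 16 × 2.828) = 8/53.2 = 15.0%.
- A reader might infer that the SAP substitutes a constant and sets the limit for that reason. It says only that values are replaced; the method is in an addendum not available here, and no reason for 15% is given.
- A reader might infer that this rule alone would leave a negative trial unexplained. If ePHex is negative and the extension closes early, SAP 7.1 already confines efficacy output to the primary and key secondary endpoints, so stool summaries would be absent anyway.

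**Conclusion.** The point holds in this form. SAP 7.6.3 makes the stool summaries, changes from baseline and plots depend on the outcome they measure, with two limits that do not agree and no denominator for the 15%. Protocol 12.7 has no such condition, and SAP section 8 does not record the departure.

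On the pooled, per-genotype reading, 11 of 72 values below LOD, or three persistently negative subjects, remove the analysis; with about 51 samples, 8 values do. These counts rest on that reading of the denominator and, for the 51, on drop-out at a constant 25% a year.

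The colonisation data themselves are not lost, since the individual listing remains, and nothing suggests that the rule was chosen to favour the product. The primary analysis is unaffected. The change should nevertheless be made: the endpoint is the pharmacodynamic check and the correction is small.

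**What to change.** In SAP 7.6.3:

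1. Whatever the share below LOD, report for each genotype, by visit and group, the number and percentage with detectable O. formigenes, and the median and quartiles with values below LOD ranked lowest. Where a quantile falls among those values, print it as below LOD.
2. Keep the plot against change in total plasma oxalate that Protocol 12.7 calls for, with values below LOD marked. SAP 12.3 lists no such figure, so it should be added there.
3. Apply any limit only to substitution-based means and changes. State one limit, and define its denominator by genotype, group, visit and study period.
4. Record the departure from Protocol 12.7 in SAP section 8.

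The cost is SAP wording and one frequency table; the plot is already promised by the protocol. No extra data are needed.
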